WA Department of Labor and Industries (DLI). The DLI State Fund provides WC insurance for over 2/3 of workers in WA (the remainder work for large self-insured companies and will be excluded due to insufficient available data). Roughly 93,000 State Fund WC claims are accepted annually. Of these, almost 20% involve time loss benefits. Of all accepted WC claims, 32% are women and 68% are men. Overall, about 21% are ≤ 24 years old at injury, 27% are 25 to 34, 24% are 35 to 44, 19% are 45 to 54, and 9% are 55 or older. Race and ethnicity are not recorded; however, in our prior research, approximately 70% of workers were white, 16% were Latino, and 13% reported other racial or ethnic backgrounds. In WA in 2016, there were over 11,000 workers with opioid prescriptions in the first 6 weeks after injury.

OH Bureau of Workers' Compensation (BWC). The BWC is the largest state-fund insurance system in the U.S. and one of the top 10 largest underwriters of WC insurance in the nation, insuring about 60% of OH's workforce. The volume of injured workers in OH is quite similar to WA. The BWC State Fund has about 90,000 accepted claims per year, and about 12% involve time loss benefits. Overall, 36% are

women and 64% are men. About 15% are \leq 24 years old at time of injury, 23% are 25 to 34, 20% are 35 to 44, 22% are 45 to 54 and 20% are 55 or older. The BWC does not collect data on race or ethnicity. In the BWC State Fund, there is an approximate annual prevalence of 20,000 opioid users.

Inclusion Criteria

Aims 1 & 2. Injured workers in OH and WA who (1) file a new accepted State Fund claim, and (2) fill at least one opioid prescription, paid for by WC, during the first 6 weeks after date of injury. The denominator for both time series described in the Analytical Methods section (Aim 1. Analysis Topic A) has the same inclusion criteria, except that criterion (2) does not apply. The same criteria—including criterion (2)—apply to the numerator for the first time series. The numerator for the second time series described is similar, except that criterion (2) is instead the presence of unsafe opioid prescribing during the subacute phase (6-12 weeks).

Aim 3 key informants. Policy makers and stakeholders who were involved in the creation and implementation of the WA or OH ORP.

Aim 3 provider in-depth interviews. Providers that had at least one patient whose opioid prescription paid for through WC had been reviewed in accordance with the state's ORP.

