OH opioid review. The OH regulations are similar to those in WA regarding best practices, but differ in approach. Rather than a “hard stop” on opioid prescription payments, an automated report identifies new opioid prescriptions beyond the acute phase. OH WC pharmacy and clinical staff review the medical record at 12 weeks to determine whether best practices were met. If not, the prescriber is notified via letter, and cases are reviewed again at 16 weeks. If best practices have still not been met, the prescriber

and worker are notified via letter that opioid coverage will end in 4 weeks. The OH program relies on retrospective chart review and communication of best practices to prescribers.

Centers of Occupational Health and Education (COHE) care delivery, in WA. The focus of the COHEs is to deliver occupational health best practices during the first 12 weeks after injury, during the transition from acute/subacute to chronic pain. The COHE delivery system has been developed over the past decade, and now approximately 50% of workers in WA receive care under these innovative arrangements. Critical elements of the COHE model include organizing care delivery on a population basis, high level executive health system support, ongoing care coordination by health service coordinators (HSCs), and stepped care management. Specific best practices include screening for psychosocial barriers to recovery using the validated Functional Recovery Questionnaire (FRQ); initiation of graded exercise; education regarding psychosocial barriers to recovery; and, more recently, a brief series of cognitive behavioral and reactivation techniques, i.e., activity coaching. COHE is a health care systems intervention, rather than a specific health care service or menu of services, that is primarily focused on improving the coordination of care at the health care community level, as well as with DLI. The COHE model consists of enhanced provider education regarding occupational health best practices and stepped-care features. Both usual care and COHE-based care in the WA workers' compensation (WC) system include the typical mix of health care services delivered for work-related injuries in Washington State, such as chiropractic care, physical therapy, evidence-based imaging services, and guideline-concordant surgery.

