1	F. Subgroup response to opioid review decisions	Subgroup analysis using PDMP data	Opioids obtained from different prescriber or different payer	OH/WA cohorts
1	G. Describe usual care	Descriptives (rates)	Health care utilization	OH/WA cohorts
2	H. PA vs RR	GEE/propensity score & subgroup analysis	Secondary outcomes	OH/WA survey samples
2A	I. COHE vs non-COHE	GEE/propensity score & subgroup analysis	Unsafe opioid prescribing	WA cohort & survey sample
2A	J. COHE vs non-COHE	GEE/propensity score & subgroup analysis	Secondary outcomes	WA survey sample

Admin, administrative data; COHE, Centers of Occupational Health and Education; GEE, generalized estimating equations; ITSA, interrupted time series analysis; OH, Ohio; PA, prior authorization; RR, retrospective review; WA, Washington.

Aim 1

Specific aim 1. Examine the comparative effectiveness of prospective prior authorization (PA) with hard stops in WA versus retrospective review (RR) with prescriber notification in OH in reducing unsafe opioid prescribing.

Hypothesis 1. Prospective PA with hard stops (WA) will be associated with statistically significantly less unsafe opioid prescribing compared to RR and prescriber notification (OH). [See Analysis Topic B]

Aim 1. Analysis Topic A: Compare long-term prescribing patterns across states and identify discontinuities

This analysis will be based on a time series approach. We will construct data points for each month from January 1, 2010 through December 31, 2020. For each state, we will construct two separate time series. The first is the proportion of WC claims with any opioid prescription in the acute phase (0-6 weeks). The second is the proportion of WC claims with unsafe opioid prescribing (defined earlier) during the subacute phase (6-12 weeks). For each, calendar month denominators for the time series will be assigned based on date of injury, and numerators will be calculated for each one-month set of claims using the pharmacy billing data for up to three months after date of injury.

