The resulting four time series will be inspected to identify secular trends and discontinuities/unexpected changes that might indicate a policy or regulatory action, or an external factor that might have affected opioid prescribing pattern. A timeline of opioid-related policy events affecting WA and/or OH (e.g., legislation, regulations, guidelines, large-scale interventions) will be constructed and overlaid on these time series to assess patterns and potential confounding related to the state-based environments. As part of Aim 3 (described below), qualitative methods will be used to understand the causes of unexplained fluctuations.

Finally, we will test whether implementation of the WA PA program (implemented in July 2013) or the OH RR program (implemented in March 2019) was associated with a statistically significant reduction in the rate of unsafe opioid prescribing using standard interrupted time series analysis (ITSA) techniques.^{1,2}

Aim 1. Analysis Topic B: Compare PA to RR with respect to unsafe opioid prescribing

This analysis is focused on the primary outcome for this study, unsafe opioid prescribing (defined earlier), using administrative data for the full WA and OH cohorts. We are planning for a one-year prospective timeframe, beginning July 2019 (based on dates of injury). Our cohort size estimates are 4,636 eligible workers in WA and 779 in OH .

Using WC claims and billing data from each state, we will track opioid prescribing for each injured worker for a full year after date of injury in order to test Hypothesis 1: Prospective PA with hard stops (WA) will be associated with statistically significantly less unsafe opioid prescribing compared to RR and prescriber notification (OH).

The primary outcome is the composite unsafe prescribing measure (i.e., meeting one or more of the 3 chronic-phase criteria in Table 1), modeled longitudinally over the three 3-month time windows, in order to assess the comparative effectiveness of PA/RR on the transition from early opioid therapy to longer-term unsafe opioid prescribing. Generalized estimating equations (GEE) panel models will be used to account for outcomes being measured during several time windows within individual patients.³

¹ Linden, A. (2015). Conducting interrupted time series analysis for single and multiple group comparisons. *The Stata Journal*, 15(2), 480-500.

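### Topic A's only unsafe-prescribing series (weeks 6-12) closes when Ohio's first described case review opens, and calendar program months are not mapped to injury months

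*Combined protocol and SAP*

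**What the plan says.** Section 7, Analysis Topic A, builds two monthly series per state from January 2010 to December 2020. The first is any opioid in the acute phase. The plan then says: "The second is the proportion of WC claims with unsafe opioid prescribing (defined earlier) during the subacute phase (6-12 weeks"). Table 4 lists the same two outcomes. Section 4 (Inclusion Criteria) agrees: for the second numerator, "criterion (2) is instead the presence of unsafe opioid prescribing during the subacute phase (6-12 weeks"). On timing, "calendar month denominators for the time series will be assigned based on date of injury", and numerators are counted "using the pharmacy billing data for up to three months after date of injury".

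The test is stated as: "we will test whether implementation of the WA PA program (implemented in July 2013) or the OH RR program (implemented in March 2019"), judged by a significant reduction in unsafe prescribing under standard interrupted time series (ITSA) methods. No injury-month break, lag or phase-in is given.

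Section 5 describes the programs. In Washington, payment for an opioid billed after week six is refused unless the prescriber has filed the attestation. In Ohio, an automated report picks up new prescriptions after the acute phase, and then "OH WC pharmacy and clinical staff review the medical record at 12 weeks to determine whether best practices were met". The next step reads: "If not, the prescriber is notified via letter, and cases are reviewed again at 16 weeks". If the practices are still unmet, prescriber and worker are told that coverage ends in four weeks.

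**The concern.** One outcome window is used to test two programs that act at different times. In Washington the whole window follows the program's action on the claim. In Ohio the window ends at the week in which the first described action on the claim begins. A null Ohio result could then be read as a failure of review, although review had not yet happened on the claims being counted.

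Topic A is a supporting analysis, but it is the only planned test with data from before the programs: Topic B's cohort starts with July 2019 injuries, after both. Topic B also tests the subacute measure across states as a separate outcome, partly to learn about the mechanism and timing of the program effects. Without a caveat, that contrast compares a program already acting on the claim with one that has not yet reviewed it.

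The second problem is the time axis. A worker injured in June 2013 reaches weeks 6-12 after Washington's July 2013 start, yet would be counted as pre-program if the break were set at July 2013.

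**Working it through.** The plan gives no power, alpha or effect size for the ITSA, so there is no figure of its own to reproduce. The check uses dates and noise-free regression.

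**1. Window against program action.** Weeks 6-12 are days 42-83, which is 42 days. The 3-6 month window is taken as days 91-181, which is 91 days. Ohio's steps are at week 12 (day 84), week 16 (day 112) and, at the earliest, coverage end at week 20 (day 140). Section 5 does not say what the 12 weeks are counted from; injury is assumed.

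| Event | Days 42-83 on or after it | Days 91-181 on or after it |
|---|---|---|
| WA payment stop, day 42 | 42/42 = 100% | 91/91 = 100% |
| OH first review, day 84 | 0/42 = 0% | 91/91 = 100% |
| OH second review, day 112 | 0/42 = 0% | 70/91 = 77% |
| OH earliest coverage end, day 140 | 0/42 = 0% | 42/91 = 46% |

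If the numerator ran to day 91, only 7 of 49 days (14%) would follow week 12.

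**2. Calendar month against injury month, if earlier injuries were covered.** For a start on the 1st:
- WA: 1 July 2013 minus 83 days = 9 April 2013 (first partly exposed injury date); minus 42 days = 20 May 2013 (first fully exposed). Shares of days 42-83 falling after the start are 20% for April injuries, 85% for May and 100% for June.
- OH: 1 March 2019 minus 83 days = 8 December 2018; minus 42 days = 18 January 2019. Shares are 23% for December, 88% for January and 100% for February.

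**3. Cost of a break at the program month.** Let y(t) be the exposed share in injury month t (a true step of 1) over 132 months. Fit y = a + b·t + c·I(t ≥ T) + d·I(t ≥ T)·(t − T) by least squares, with and without the d term. The understatement is 1 − c. Ranges cover every start day in the program month and four exposure rules (any exposed day, proportional, at least half, whole window).

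| Subacute series | c, level-plus-slope | c, common slope |
|---|---|---|
| WA, earlier injuries covered | 0.75-0.96 | 0.88-0.98 |
| OH, change by calendar date in March 2019 | 0.90-0.98 | 0.89-0.98 |
| WA, new injuries only, start on 1 July / 31 July | 1.00 / 0.96 | 1.00 / 0.95 |
| OH, new injuries only, start on 1 March / 31 March | 1.00 / 0.84 | 1.00 / 0.95 |
| OH, change only after first letters on March injuries | 0.62-0.995 | 0.88-0.998 |

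The last row uses 1 March + 84 days = 24 May 2019 to 31 March + 84 days = 23 June 2019.

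With earlier injuries covered, excluding April-June 2013 (WA) or December 2018-February 2019 (OH, change by calendar date) gives c = 1.00. With new injuries only, excluding the program month gives 1.00. For Ohio, a June 2019 break with December 2018-May 2019 excluded gives 1.00 under both the calendar-date and the first-letter routes.

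**4. Ohio precision at 3-6 months (illustrative).** Topic B expects 779 Ohio workers a year, so 779/12 = 64.9 a month. Assumed event rates of 5%, 10% and 20% give 3.2, 6.5 and 13.0 events a month. The detectable step is (1.96 + 0.84) × SE(c) divided by the mean, with variance equal to the mean. With 104 pre and 22 post months this gives 72%, 51% and 36% (level-plus-slope) or 51%, 36% and 25% (common slope).

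**The case against.** The strongest reply is that Topic A asks about program implementation, not about review of individual claims. A program can change prescribing before week 12. Section 5 says "The OH regulations are similar to those in WA regarding best practices, but differ in approach", so prescribers may respond to the rules themselves or anticipate review. The Clustering text expects providers to carry their experience over to other patients. The automated report may also flag claims before week 12, although no notice to the prescriber is described at that step. All of this stands. A reader might infer that the Ohio ITSA is uninformative or invalid; the documents do not support that, because it remains a fair test of a program-level change in weeks 6-12.

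A reader might also infer that the test of Hypothesis 1 is compromised. It is not: that hypothesis is tied to Topic B, whose primary composite covers 3-12 months, after Ohio's first review.

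Nor are the program dates missing. July 2013 and March 2019 are stated; what is missing is their mapping to injury months. The plan calls itself tentative, but ties updates to data availability and cross-state comparability, whereas this issue follows from program rules already written down.

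Finally, the added Ohio series would be imprecise. That is a fair limit. The 3-6 month figures rest on an event rate found in no document, flat volume back to 2010 and no autocorrelation. They also use a cohort with an early opioid fill, which Topic A's subacute numerator does not require.

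**Conclusion.** The point holds as an issue of interpretation and specification that should be fixed before analysis. None of the 42 outcome days in Ohio follows the first described review of the same claim; in Washington all 42 follow the payment stop. The Ohio subacute ITSA and Topic B's subacute state contrast therefore do not test the direct effect of Ohio review, and a null in the former is not evidence that review failed. This assumes that the 12 weeks run from injury.

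The size of the break error depends on each program's reach, which the plan does not state. Section 5 words the Washington rule by when the prescription is billed, with no injury-date limit, which suggests that earlier injuries were covered. In that case the understatement of an immediate step is about 4-25% in Washington and 2-10% in Ohio (2-12% and 2-11% with a common slope). If only new injuries were covered, it is zero for a start on the 1st, rising to 4-5% (Washington) or 5-16% (Ohio) for a start on the 31st. If Ohio prescribing moved only after first letters, it could be 0-38% (0-12% with a common slope).

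**What to change.** 1. Keep the subacute series and add, per state, a 3-6 month series from Table 1: the composite, or its component of at least 60 days supply if dose or sedative fields do not reach back to 2010. Report it with confidence intervals as the series able to reflect Ohio review.
2. State that the Ohio subacute ITSA and Topic B's subacute contrast do not test the direct effect of Ohio review.
3. Before seeing the data, record each program's start day and whether it applied to earlier injuries. Exclude as phase-in every injury month whose outcome window is only partly exposed, or is exposed before the break. That includes the program month itself if only new injuries were covered and the start was after the 1st. If earlier injuries were covered, the exclusions are:
   - WA subacute: April-June 2013.
   - WA 3-6 months: January-June 2013.
   - OH subacute: December 2018-February 2019.
   - OH 3-6 months: December 2018-February 2019 if only claims reaching week 12 after the start were reviewed, or September 2018-February 2019 if older claims were too.
4. Run one Ohio subacute sensitivity analysis with a June 2019 break, excluding December 2018-May 2019.

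The cost is SAP wording, analysis time and a pharmacy extract of six months after injury instead of three for 2010-2020 claims (to about 1 July 2021). Topic B's extract does not cover this. A few points are lost: under the exclusions in item 3, WA subacute goes from 42/90 to 39/90 pre/post months and OH subacute from 110/22 to 107/22 (107/19 in the sensitivity analysis). Ohio precision at 3-6 months is limited, with detectable steps of 25-72% on the illustrative assumptions, so a null there must be read with its interval. Some asymmetry remains, since only 46% of that window follows Ohio's earliest coverage end.

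### Topic A's interrupted time series commits to no concurrent control, and its 6–12 week outcome closes just as Ohio's chart review begins

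*Combined protocol and SAP*

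**What the plan says.** Topic A builds two series per state: any acute-phase opioid prescription, and unsafe prescribing in weeks 6–12. "We will construct data points for each month from January 1, 2010 through December 31, 2020". Months are assigned by date of injury, and numerators are counted "using the pharmacy billing data for up to three months after date of injury". The plan then tests whether the WA program (July 2013) or the OH program (March 2019) "was associated with a statistically significant reduction in the rate of unsafe opioid prescribing using standard interrupted time series analysis (ITSA) techniques". Only the second series measures unsafe prescribing, so that is the series tested.

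The method is described no further than as standard. There is no model equation, control series, scale, lag, or handling of autocorrelation or seasonality. Topic A also plans inspection of the series, an overlaid policy timeline and qualitative follow-up of unexplained fluctuations.

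Section 5 says that WA denies payment past week six unless the prescriber files a checklist. In OH, pharmacy and clinical "staff review the medical record at 12 weeks to determine whether best practices were met".

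**The concern.** There are two separate problems.

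First, an interrupted time series (ITSA) fitted to one state compares what followed the program with a continuation of that state's own earlier trend. Anything else that bends or shifts the series after the start date enters the estimate. OH has few post-program months, so a late event affecting both states would weigh heavily there. WA has a short pre-period from which to learn the shape of its trend. Each state could serve as a comparison for the other, because neither program starts near the other's date, but the plan does not commit to using it.

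Second, the outcome window suits one program and not the other. A finding that WA's program reduced unsafe prescribing and OH's did not could arise because weeks 6–12 contain WA's intervention and precede OH's.

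**Working it through.** The plan gives no power, alpha or effect size for this analysis, so there is no figure to reproduce.

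**Month counts** (dates from Topic A)
- Total: 11 × 12 = 132.
- WA before: 3 × 12 + 6 = 42. After: 132 − 42 = 90.
- OH before: 9 × 12 + 2 = 110. After: 132 − 110 = 22.
- Gap between the two dates: 110 − 42 = 68 months.

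**Simulation with no program effect.** Monthly claims follow section 4: WA 93,000/12 = 7,750 and OH 90,000/12 = 7,500. The documents give no subacute rate, so these are assumptions: a starting rate of 2% or 4%, a fall of about 80% over 2010–2020, the same curve in both states, independent months, and two-sided 0.05. The single-state model is

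E(y_t) = b0 + b1·t + b2·D_t + b3·D_t·(t − k), with D_t = 1 from interruption month k.

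The two-state model fits these terms to both states and tests state × D_t and state × D_t·(t − k). Fits are weighted by binomial variance. A false reduction is a significantly negative level or slope term. Each pair below gives the 2% and 4% starting rates, from 2,000 runs.

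| Shared pattern | Test | Single-state | Other state as control |
|---|---|---|---|
| Linear decline | OH | 5%, 4% | 4%, 5% |
| Linear decline | WA | 5%, 4% | 5%, 5% |
| Linear, 10% drop from Jan 2020 | OH | 20%, 33% | 4%, 6% |
| Linear, 20% drop from Jan 2020 | OH | 55%, 85% | 5%, 4% |
| Linear, 10% drop from Mar 2019 | OH | 38%, 62% | 5%, 5% |
| Linear, 20% drop from Mar 2019 | OH | 92%, 99.7% | 5%, 4% |
| Exponential decline | WA | 25%, 41% | 3%, 3% |
| S-shaped decline, centred mid-2015 | WA | 100%, 100% | under 1% |

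Three limits apply.
- Curvature in OH has no single answer. The exponential curve and the S-curve centred mid-2015 gave 0% false OH reductions; S-curves centred in 2017 or later gave 97% to 100% false level drops.
- The control works here because the curves are identical. With WA's S-curve leading OH's by 12 months, the two-state test gave false level reductions in 78% to 99% of runs in the settings tried. The size depends on the curve and the variance estimate.
- Variance estimation matters with 22 months. Newey–West errors (lag 6) under the shared linear decline gave about 20% false OH reductions with or without a control.

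**Outcome window against program timing** (section 5)

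| Weeks after injury | WA | OH |
|---|---|---|
| 6–12 (tested series) | Payment stop in force | Automated report flags prescriptions; no chart review yet |
| 12 | | Chart review, letter if needed |
| 16 | | Second review, notice if needed |
| 16 + 4 = 20 | | Coverage ends |

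The 3–6 month window (roughly weeks 13–26) contains the OH steps after the first review.

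**Alignment.** If the OH program began on 1 March 2019 (only the month is given) and covered open claims (not stated), injuries from about 18 January 2019 (42 days earlier) have their whole 6–12 week window after the start. Injuries from about 7 December 2018 (84 days earlier) reach the week-12 review after it. The plan indexes months by injury date and sets no lag.

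**The case against.** The strongest reply is that the plan leaves the model open and does not choose a weak one. Topic A's heading speaks of comparing states, the first cited method paper covers single and multiple groups by its title, and section 7 calls the plan tentative until OH data are seen. That stands. A reader might infer that each program will be tested only against its own extrapolated trend, but the text does not say so. The supportable point is that no concurrent control is committed to.

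A reader might also infer a large background fall in the tested outcome. Section 4 says that in WA in 2016 "there were over 11,000 workers with opioid prescriptions in the first 6 weeks after injury", against an expected 4,636 in the cohort from July 2019: 1 − 4,636/11,000 = 58%. But these are WA acute-phase counts under different eligibility criteria. They establish nothing about subacute proportions or about OH. Nor is every shared trend a threat, since a linear one is modelled.

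It would go too far to call the OH test blind. An automated report flags prescriptions after the acute phase, and the Clustering section expects providers to change practice for other patients, so later claimants' weeks 6–12 could respond.

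Inspection, the timeline and interviews make a naive reading less likely. They do not change the estimate or its p-value, and section 8 says current and former employees of the OH agency cannot be interviewed.

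Finally, replacing the single-state fits with the two-state contrast is not safe. Section 2 of the plan's own background describes WA as acting earlier than OH, so parallel trends cannot be presumed.

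**Conclusion.** Both points hold. The exposure to a shared shock in the OH test is substantial across the shock sizes and starting rates tried. The WA exposure depends on the trend being curved. These sizes rest on assumed rates and shapes and on parallel states, so they show direction and range and do not predict the result.

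The window problem needs no simulation: it follows from the stated timings. As planned, the OH result cannot speak to the direct effect of chart review, and the two states' results are not like for like.

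The consequence is confined to Topic A's program-effect claims.

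**What to change.** 1. Add a chronic-phase (3–6 month) unsafe-prescribing series in both states and use it for the OH interruption. Align the interruption month to injury date and review timing, and state any lag.
2. Report a two-state comparative ITSA, with state-by-level and state-by-slope contrasts at each date, alongside the single-state fits. Check parallel pre-trends and state how autocorrelation and seasonality are handled. Consider a log or logit scale; an exponential decline is a straight line on the log scale. Claim a program effect only where the two analyses agree or the pre-trends are parallel.
3. Repeat the OH test with the post-period cut before any late shock identified on the policy timeline.

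The cost is SAP wording, a few more models on series already planned, and three more months of billing follow-up (to about the end of June 2021 for December 2020 injuries). The downsides are wider intervals and a control that can itself mislead if the states' trends are not parallel.
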